6.1 Efficacy Assessments

6.1.1 Psoriasis Area and Severity Index Score

The PASI score will be assessed as described by Langley and Ellis (2004). The PASI is a physician assessment that combines the assessment of the severity of and area affected by psoriasis into a single score in the range 0 (no disease) to 72 (maximal disease). The absolute PASI score in this study is used as part of inclusion criterion #4. The PASI percentage response rates are efficacy endpoints (ie, PASI-50, PASI-75, PASI-90, and PASI-100). For example, the percentage of participants who achieve a 75% or greater reduction in PASI score from baseline is represented by the PASI-75 value. Details of the PASI assessment will be provided in the relevant training material.

Response Definitions based on PASI score at Week 16:

- **Responders:** Participants on treatment achieving PASI-50 or greater at Week 16 visit
- **Relapse:** Increase in PASI score to baseline value or greater, or participant begins a new treatment for psoriasis
- **Partial Relapse:** Loss of PASI-50 response after cessation of study treatment
- **Rebound:** Increase in PASI score to 125% of baseline value or above, or onset of new pustular/erythrodermic psoriasis within 3 months of cessation of study treatment
- **Duration of remission:** Time from first achievement of PASI-100 to loss of PASI-100
- **Duration of treatment success:** Time from first achievement of PASI-50 to loss of PASI-50
- **Duration of therapeutic effect:** Time from cessation of study treatment until increase of PASI to 50% of maximum improvement from baseline

6.1.2 Lesion Severity Score

The LSS is used to score the severity of psoriasis plaques (Patel and Tsui 2011). The dimensions of scaling, erythema, and plaque elevation are each scored on a scale from 0 to 4, and the total LSS is the numerical sum of the 3-dimensional scores observed at a single study visit.

6.1.3 Physician's Global Assessment

The National Psoriasis Foundation Psoriasis Score version of a static PGA is calculated by averaging the total body erythema, induration, and desquamation scores (Feldman and Krueger 2005). Erythema, induration, and desquamation will be scored on a 6-point scale, ranging from 0 (clear) to 5 (severe): the total PGA score is defined as the average of the erythema, induration, and desquamation scores. Details of the PGA assessment will be provided in the relevant training material.

6.1.4 Percent of Body Surface Area Involvement

The percent of BSA involvement will be estimated for each participant, where 1% is approximately the area of the participant's handprint (Walsh et al 2013). Details of the BSA assessment will be provided in the relevant training material.

Walsh and colleagues proposed the product of the PGA and the BSA involvement as a simple and effective alternative for measuring severity of psoriasis in clinical trials (Walsh et al 2013).

6.1.5 Modified Nail Psoriasis Severity Index

The mNAPSI is a numeric, reproducible, objective, and simple tool for physicians to evaluate the severity of nail bed psoriasis and nail matrix psoriasis by area of involvement in the nail unit (Cassell et al 2007). Details of conducting the mNAPSI will be provided in the relevant training material.

6.1.6 Dermatology Life Quality Index

The DLQI is a patient reported outcomes instrument for assessing the impact of dermatologic conditions on patients' quality of life (Finlay and Khan 1994).

6.1.7 Psoriasis Symptom Inventory

The PSI is a patient reported outcomes instrument that is used to assess the severity of plaque psoriasis symptoms (Bushnell et al 2013). All symptoms (itch, redness, scaling, burning, cracking, stinging, flaking, and pain) are rated on a 5-point severity scale. The PSI demonstrated good construct validity and was sensitive to within-subject change ($p<0.0001$). Details of administering the PSI will be provided in the specific user manual.

6.1.8 Pain

Pain will be assessed by the SF-36 BPS and the VAS Pain (Hawker et al 2011).

6.1.9 Fatigue

Consistent with a recent study of fatigue in psoriasis (Skoie et al 2017), fatigue will be assessed by the vitality subscale of the SF-36 (van der Heijden et al 2003) and a fatigue VAS (Wolfe 2004).

6.1.10 Biopsy of Skin Plaque

Skin plaque biopsies (ie, a 4 mm punch biopsy, performed pre-dose by suitably trained study personnel and processed as per laboratory manual) are to be performed after all other assessments have been completed at the end of Visits 2 and 10.

6.2 Safety and Tolerability Assessments

6.2.1 Adverse Events

6.2.1.1 Definitions

6.2.1.1.1 Adverse Events

The investigator is responsible for reporting all AEs that are observed or reported during the study, regardless of their relationship to the study drug or their clinical significance.

An AE is defined as any untoward medical occurrence in a participant enrolled into this study regardless of its causal relationship to the study drug. Participants will be instructed to contact the investigator at any time after randomization if any symptoms develop.

A TEAE is defined as any event not present before exposure to the study drug or any event already present that worsens in either intensity or frequency after exposure to the study drug.

6.2.1.1.2 Serious Adverse Events

An SAE is defined as any event that

- results in death
- is immediately life threatening
- requires inpatient hospitalization or prolongation of existing hospitalization
- results in persistent or significant disability/incapacity
- is a congenital anomaly/birth defect

Important medical events that may not result in death, be life threatening, or require hospitalization may be considered SAEs when, based upon appropriate medical judgment, they may jeopardize the participant or may require medical or surgical intervention to prevent one of the outcomes listed in this definition. Examples of such medical events include allergic bronchospasm requiring intensive treatment in an emergency room or at home, blood dyscrasias or convulsions that do not result in inpatient hospitalization, or the development of drug dependency or drug abuse.

6.2.1.1.3 Suspected Unexpected Serious Adverse Reactions

A SUSAR is a serious adverse reaction, the nature or severity of which is not consistent with the applicable product information (eg, IB for an unapproved IMP). By definition, an adverse reaction is considered causally related to the study drug.

6.2.1.1.4 Adverse Events of Special Interest

There are no prespecified AEs of special interest for this study.

6.2.1.2 Eliciting and Documenting Adverse Events

Adverse events will be reported from the date of signed informed consent and through for 28 days after cessation of dosing. Adverse events occurring after the 28 days post-treatment would only be reported if the investigator considers it to be related to the study treatment.

If the investigator learns of any SAE, including a death, at any time after a participant has been discharged from the study, and he/she considers the event to be reasonably related to the study drug or study participation, the investigator must promptly notify the sponsor (or designee).

Serious AEs that occur more than 30 days after the last dose of study drug need not be reported unless the investigator considers them related to the study drug.

At every study visit, participants will be asked a standard nonleading question to elicit any medically related changes in their well-being. They will also be asked if they have been hospitalized, had any accidents, used any new medications, changed concomitant medication regimens (prescription or OTC medications), noticed any changes in bowel habits, or had unplanned visits to their general practitioner since the last visit.

In addition to participant observations, AEs identified from any study data (eg, laboratory values, physical examination findings, ECG changes) or identified from review of other documents (eg, participant diaries) that are relevant to participant safety will be documented on the AE page in the eCRF.

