After the planned 16 weeks of treatment, all participants will have an initial follow-up visit at Week 20 (ie, 4 weeks post last dose of study treatment), completing Part A of the study; and enter Part B with continued follow-up for a maximum of 20 additional weeks (up to Week 40). The duration of follow up will depend on the initial response to study therapy and any relapse or rebound experienced after cessation of study treatment.

The maximum planned duration of study participation will be 44 weeks, and the duration of the study is defined for each participant as the date signed written informed consent is provided through to their last follow-up visit. Participants will be considered to have completed the study after the completion of all required visits.

The EOS is defined as the date of the last visit of the last participant in the study or last scheduled procedure shown in the SoA.

Figure 3-1 **Study Design**

Note: All dosing is once daily.

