Samples for blood biomarkers		X								X	
BSA involvement (%), PGA, PASI ^{n, o}	X	X	X	X		X		X	X	X	X
LSS, mNAPSI ⁿ		X	X	X		X		X	X	X	X
PSI, DLQI, PA-VAS, SF-36 (vitality and pain), Fatigue ^p		X	X	X		X		X	X	X	X
AE/SAE review	X	X	X	X	X	X	X	X	X	X	X
Concomitant medication review	X	X	X	X	X	X	X	X	X	X	X
Dispense dosing diary		X	X	X	X	X	X	X	X		
Collect/review dosing diary ^q			X	X	X	X	X	X	X	X	

^a Participants who withdraw from the study during Part A should complete the final assessments listed under the Follow-up Visit (Week 20), at an unscheduled follow-up visit. Where relevant and when possible, this should be arranged within 72 hours of the start of a new psoriasis treatment. In the event of early withdrawal from the study, unused study drug is to be collected/collected at this visit.

^b All participants will attend additional follow-up Visits 12 and 13 (see Table 6-2), unless they are considered a 'treatment failure' or meet the criteria for rebound.

^c Recheck inclusion/exclusion criteria at Baseline, before first dose of study drug. Screening laboratory results will be used to confirm eligibility at Baseline/Visit 2 (ie, Day 1).

^d Predose optional genetic samples.

- e BMI will be calculated from the height and weight.
- f Women of child-bearing potential only. Serum HCG at screening, urine thereafter. Pregnancy testing will be performed at the visits indicated or if a menstrual cycle is missed or if pregnancy is otherwise suspected.
- g Participants will fast for at least 8 hours before glucose and lipid blood sampling
- h A single ECG tracing is to be obtained on the day of the visit. If, in the opinion of the investigator, there appear to be clinically significant findings, a second tracing should be obtained during the visit.
- i Blood pressure, pulse, respiratory rate, and temperature are to be checked on the day of the visit.
- j The first dose will be given at the baseline visit, following random assignment to treatment. Subsequent doses are to be taken (away from the study site) once daily in the morning at approximately the same time ± 2 hours. Participants should refrain from consuming acidic drinks 1 hour either side of dosing and from eating 2 hours before dosing and 1 hour after dosing. On days of study site visits during the treatment period (Visit 3 through Visit 10, inclusive), participants may dose at home.

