5.3.4.2 Treatment-Emergent Adverse Events

An adverse event (AE) will be classified as ‘treatment-emergent’ if the onset date/time was on or after the start date/time of study treatment. Where dates or times are missing or partially missing, AEs will be assumed to be treatment-emergent, unless there is clear evidence (through comparison of partial dates/times, see [Section 7.3.1](#)) to suggest that the AE started prior to dosing.

AEs will be classified into the following study phases based on the onset date/time of the AE after any imputations:

- Pre-Treatment Phase: All AEs with onset date/time prior to the first dose of randomized study treatment
- Treatment Phase: All AEs with onset date/time at the time of or after the first dose of randomized study treatment (Day 1) up to and including the date of the last dose of treatment received.
- Follow-up Phase: All AEs with onset date after the date of the last dose of treatment received.

For participants who complete 16 weeks of dosing per protocol the Treatment Phase will be from Day 1 to Day 112 and the Follow-up Phase will be from Day 113 until their last day in the study. In all cases the day will be assumed to start at 00:00 hours and end at 23:59 hours. Adverse events occurring in both the Treatment Phase and Follow-up Phase are classified as treatment emergent.

For the primary analysis which considers only data collected in Part A, only events which start on or prior to the end of Part A date will be included in the adverse event summaries.

The onset phase of all AEs will be included in the relevant data listings.

For the final analysis, only treatment related events which start in Part B will be included in the adverse event summaries.

Only treatment related events which start in Part B and any Part A AEs which change in Part B will be included in the relevant data listings.

6 Sample Size

The sample size of 225 participants in total, has been chosen to explore the tolerability and safety of EDP1815. Although the study will use a model-based probability inference approach in a Bayesian framework, the following power calculation was also performed (using a basic frequentist approach) in order to give confidence that enough participants are available to find a clinically meaningful difference between active dose and placebo if the below assumptions are met.

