10.2 Adverse Events

Adverse events will be reported from the date of signed informed consent and through for 28 days after cessation of dosing. Adverse events occurring after the 28 days post-treatment would only be reported if the investigator considers it to be related to the study treatment.

Only treatment emergent AEs (TEAEs) will be included in the summaries, pre-treatment AEs will be included in the listings of all AEs.

In the primary analysis at the end of Part A, only adverse events which started on or before date of the end of Part A will be included in the summaries.

In the final analysis at the end of Part B, only adverse events which started during Part B will be included in the summaries. Treatment related events which start in Part B and any Part A AEs which change in Part B will be included in the relevant data listings.

All AEs will be coded using version 23.0 of MedDRA. Severity of event will be coded using the Common Terminology Criteria for Adverse Events v5.0 (CTCAE).

An overview of TEAEs will be produced showing the number and percentage of participants with:

- Any TEAEs (Part A)
- Any TEAE of CTCAE grade 2 or above (Part A)
- Any TEAE of CTCAE grade 3 or above (Part A)
- Any TEAE of CTCAE grade 4 or above (Part A)
- Any fatal TEAE (Part A)
- Any serious TEAE (Part A)
- Any TEAE leading to permanent discontinuation of study drug (Part A)
- Any TEAE leading to withdrawal from the study (Part A)
- Any related TEAE (Part A and Part B)
- Any related TEAE of CTCAE grade 2 or above (Part A and Part B)
- Any related TEAE of CTCAE grade 3 or above (Part A and Part B)
- Any related TEAE of CTCAE grade 4 or above (Part A and Part B)
- Any related fatal TEAE (Part A and Part B)
- Any related serious TEAE (Part A and Part B)
- Any related TEAE leading to permanent discontinuation of study drug (Part A and Part B)
- Any related TEAE leading to withdrawal from the study (Part A and Part B)

Related events are those which were considered by the investigator to be possibly, probably or definitely related to study drug.

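### The 28-day limit on all-cause adverse event collection conflicts with the Week 20 safety visit, the 30-day limit for serious events, and the rules to record events regardless of relationship

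*Protocol*

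**What the plan says.** Protocol 6.2.1.2 sets the general rule: "Adverse events will be reported from the date of signed informed consent and through for 28 days after cessation of dosing". It continues: "Adverse events occurring after the 28 days post-treatment would only be reported if the investigator considers it to be related to the study treatment". SAP 10.2 opens with the same two statements.

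Two paragraphs later, protocol 6.2.1.2 gives a different limit for serious events: "Serious AEs that occur more than 30 days after the last dose of study drug need not be reported", unless the investigator considers them related. Protocol 6.4 also uses 30 days after the last dose, for repeating clinically significant abnormal laboratory tests.

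The same protocol contains rules with no relatedness condition:

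- 6.2.1.1.1 makes the investigator responsible for all adverse events seen or reported during the study, whatever their relationship to study drug.
- The last paragraph of 6.2.1.2 has adverse events identified from laboratory, examination or ECG data documented in the eCRF.
- 6.2.1.2.2 requires reporting whatever the causality assessment.
- 6.4 has abnormal laboratory results and other abnormal safety assessments recorded as AEs or SAEs, except those associated with the underlying disease and no more severe than expected.

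On timing, SAP 5.3.4.2 states "For participants who complete 16 weeks of dosing per protocol the Treatment Phase will be from Day 1 to Day 112". Protocol Table 6-1 puts Visit 11 (Week 20) at Day 141 with a window of Day 141 to 148, and schedules physical examination, laboratory tests, ECG, vital signs and AE/SAE review there. Table 6-2 (Part B) has no row for any of these. Protocol 3.1 describes the timing this way: "all participants will have an initial follow-up visit at Week 20 (ie, 4 weeks post last dose of study treatment".

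For the primary analysis, SAP 10.2 states that "only adverse events which started on or before date of the end of Part A will be included in the summaries". Its overview table shows treatment-emergent events of any cause for Part A, and only related events for Part A and Part B together.

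**The concern.** Three boundaries that ought to coincide do not: the end of all-cause collection (28 days off drug), the end of all-cause serious event collection (30 days), and the end of Part A (Visit 11), which is where the SAP cuts its tables. The planned off-drug safety visit falls on or just beyond the first boundary.

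The stake is consistent ascertainment. Safety is part of the primary objective (protocol 2.1), and there is no safety review or data monitoring committee (protocol 11.1.1). If one site records an unrelated abnormality first seen at Visit 11 under protocol 6.4 and another leaves it out under the 28-day rule, the Part A tables depend on which paragraph each site followed.

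Participants who stop drug early but stay in the study raise a second issue. Protocol 4.2.1 encourages them to keep attending, and AE review is scheduled at every Part A visit, but their all-cause collection ends 28 days after their own last dose. If early stopping differs between arms, so will the length of follow-up under the narrower rule.

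**Working it through.** **Last dose of a completer.** Sixteen weeks of daily dosing from Day 1 ends on Day 1 + 16 × 7 − 1 = 112. This reproduces the SAP 5.3.4.2 figure.

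That day is not fixed. Table 6-1 footnote j says "On days of study site visits during the treatment period (Visit 3 through Visit 10, inclusive), participants may dose at home", and the Visit 10 window is Day 110 to 116. The Dosing row of Table 6-1 has no mark at Visit 10, so the table and its footnote also need reconciling. The 4-week description in protocol 3.1, counted back from the nominal visit day, gives 141 − 28 = Day 113. A range is therefore used.

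**Limits against the Visit 11 window (Day 141 to 148, 8 days).** AE limit = last dose + 28. SAE limit = last dose + 30.

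| Last dose | AE limit | Window days inside | SAE limit | Window days inside |
|---|---|---|---|---|
| Day 110 | Day 138 | 0 of 8 | Day 140 | 0 of 8 |
| Day 112 | Day 140 | 0 of 8 | Day 142 | 2 of 8 |
| Day 113 | Day 141 | 1 of 8 | Day 143 | 3 of 8 |
| Day 116 | Day 144 | 4 of 8 | Day 146 | 6 of 8 |

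With a last dose on Day 112, Visit 11 falls 141 − 112 = 29 to 148 − 112 = 36 days off drug. Covering the whole window under the 28-day rule would need a last dose on Day 148 − 28 = 120, which is after the Visit 10 window closes.

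**AE limit against SAE limit.** A serious adverse event is also an adverse event. An unrelated one on day 29 or 30 off drug is outside the 28-day rule, while the serious event rule releases it only after day 30. This conflict holds whatever the last-dose day.

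**Early stop with continued visits.** Take a last dose at the nominal Week 4 visit, Day 29. All-cause collection ends on Day 29 + 28 = 57. From there to nominal Visit 11 is 141 − 57 = 84 days, or 12 weeks, of related-only collection. The Part A tables count events over that whole period.

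**The case against.** The tempting stronger reading is that an unrelated finding at Visit 11 becomes an adverse event only if judged related, and so is lost. The documents do not support that, for three reasons.

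- The four passages listed above set no relatedness condition, and one is in the same section as the 28-day rule. They show a conflict, not a settled exclusion.
- The limit concerns events occurring after 28 days, not events detected after it. Protocol 6.2.1.2 has participants asked about changes since the last visit, so Visit 11 still picks up events with earlier onset. Nothing says that an abnormality first seen at Visit 11 has its onset that day; the onset rule is simply absent.
- SAP 10.5, 10.6.1 and 10.6.2 summarise laboratory, ECG and vital-sign values by visit, with shift tables to the worst post-baseline value. Those outputs need no adverse event record.

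It can also be said that related-only collection after a fixed off-drug period is a deliberate choice, applied alike to all blinded arms and restated in SAP 10.2. The treatment-phase table ends at the last dose and is unaffected. Those points stand. They do not remove the 28-versus-30-day conflict, the opposing instructions for Visit 11, or the change of basis within the overall and follow-up-phase tables.

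Finally, a reader might turn the 15% in protocol 7.3 into a count of people with incomplete safety follow-up. That figure is for treatment discontinuation, not study withdrawal, so it gives no such count.

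**Conclusion.** The passages contradict one another and should be reconciled. The 28-day limit covers between 0 and 4 of the 8 Visit 11 window days for last doses from Day 110 to Day 116, and none on the SAP's own Day 112. The AE and SAE limits differ by two days. A participant who stops drug at Week 4 and stays on visits has about 12 weeks of related-only collection inside tables that count all treatment-emergent events to the end of Part A.

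The coverage result rests on the last-dose day; the 12 weeks rest on nominal visit days. How many events would be recorded differently cannot be estimated from the documents. What is at risk is uniform recording and classification of adverse events off drug, not the underlying safety measurements.

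**What to change.** In protocol 6.2.1.2 and SAP 10.2, use one limit for all adverse events, serious or not: collect regardless of cause from consent through completion of Visit 11 (Week 20) or 30 days after the last dose, whichever is later, and related events only after that. Abnormalities first detected at Visit 11 are then recorded under the same rule. This puts the change of rule at or after the end of Part A, where the SAP overview already moves from events of any cause to related events only, and it agrees with the 30-day period in protocol 6.4.

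The cost is amendment and SAP wording, and a few more unrelated events recorded.

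One addition is optional. Participants who withdraw during Part A have their Week 20 assessments early (Table 6-1 footnote a: "Where relevant and when possible, this should be arranged within 72 hours of the start of a new psoriasis treatment"), with no later contact scheduled. A telephone contact near the end of the collection period would close that gap, but it is an extra procedure and the reconciliation does not depend on it.
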